"Serious Hypersensitivity such as Anaphylaxis and Infusion Reaction" is an important identified risk on Risk Management Plan (RMP) for Xevudy. The incidence rate of patients experiencing events correspond to Hypersensitivity (narrow) in Standardised MedDRA Queries (SMQs) within Xevudy group for 29 days was 1.7% (9/523 patients) in the global phase II/III clinical study for patients with mild to moderate infections (COMET-ICE Study). A total of 600 patients as a safety analysis set is required to monitor the incidence rate of event-experiencing patients in the post-marketing surveillance (PMS), with estimation accuracy that enables a power of \geq 80 % to detect an odds ratio of 2 for the 1.7% threshold, in case where there is the twofold real risk of the threshold. Accordingly, it is thought to be possible to examine the incidence rate in the drug use investigation of 630 patients.

5. Planned Number of Medical Institutions by Department

Approximately 30 medical institutions which provide SARS-CoV-2 infection treatment, mainly medical institutions designated for infectious diseases, regional medical care support hospitals and special functioning hospitals

6. Study Period

- 1. Study conduct
- 1) Study period: November 2021 to October 2023
- 2) Observation period:

The observation period per patient will be between Day 1 to 29 counting the date of Xevudy administration as Day 1 (28 days from the day following Xevudy administration or Day 2). If inpatients have been discharged/transferred from hospital before Day 29, they will be observed until the discharge/transfer date. For outpatients, the observation will be conducted on Day 1 only.

3) Scheduled enrolment period: January 2022 to June 2023

However, if the number of enrolled patients has reached the target sample size, enrolment may be terminated even before the completion of the above-mentioned scheduled enrolment period.

 Study end Time for final analysis to complete: June 2024 Time for final report writing to complete: December 2024

7. Study Methods

In this study, an electronic data capture (EDC) system will be used to enroll patients and collect data.

- 1. Request and contract for the study
 - The medical representative (MR) will explain the objectives, target population, study items, study methods, etc. to the planned physicians for the study, etc. at the medical institutions to which Xevudy is supplied and will request them to cooperate with the study.

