Whether or not combination therapies for exacerbation of SARS-CoV-2 infection are introduced, name of therapies (invasive mechanical ventilation (IMV) management, extracorporeal membrane oxygenation (ECMO), OA, etc.), name of therapies and date of combination therapies introduced, oxygen flow rate (maximum flow rate during the observation period) (L/min) and date of maximum flow rate introduced

<Inpatient only> Vital signs
 Highest body temperature (°C) and lowest percutaneous oxygen saturation (SpO₂) (%) and
 date of measurement at Day 1, Days 2-15 (every day), Day 22, Day 29 and the
 discharge/transfer date. On Day 1, the highest body temperature and the lowest SpO₂ will be
 selected from values which are measured before Day 1.

¹ See Guidelines for Diagnosing Patients with Novel Coronavirus Infection (COVID-19) (Guidelines Review Committee).

9. <Inpatient only> Clinical symptoms (cough without sputum (nonproductive cough), cough with sputum (productive cough), fatigue, dysgeusia, olfactory dysfunction, headache, dyspnea, sore throat, diarrhea, nasal discharge, arthralgia/myalgia), symptom of pneumonia Presence or absence of clinical symptoms and date of observation at Day 1, Days 2-15 (every day), Day 22, Day 29 and the discharge/transfer date. If any of these clinical symptoms have been identified at the date of each observation, select the clinical symptoms applicable to these.

If a symptom is not identified at Day 1 but newly occurs after Day 1 or a symptom is identified at Day 1, disappears after Day 1 and reoccurs, the symptom should be recorded into adverse events (AEs) section of the case report form (CRF) in case where it is assessed as an AE.

10.<Inpatient only> Admission status into high care unit (HCU) or intensive care unit (ICU) during observation period

Whether or not a patient is admitted into HCU or ICU and date of admission

11.Status at the end of the observation

End date of observation, inpatient outcome (hospitalization, discharge, transfer, and the reason), and whether or not a patient has died from exacerbation of SARS-CoV-2 infection and the reason

12.Pregnancy

(For female patients) whether or not a patient is pregnant during the observation period, estimated delivery date

In addition, the follow-up investigation should be conducted for a mother and her foetus as far as possible regarding the course of delivery, spontaneous abortion, elective abortion, and AEs, etc.

13.Breastfeeding

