(For female patients) Whether or not a patient feeds breast milk during the observation period 14.Adverse event (AEs)

Presence or absence of AEs after Xevudy administration, diagnosis or symptoms, occurrence date, outcome of AEs, outcome date (outcome date confirmed), seriousness, reason for assessing as serious, relationship to Xevudy, factors suspected of being related to AEs except for Xevudy

- i). To grasp the safety specification and ADRs/AEs, the investigator will collect the information about all AEs (e.g., a disease, symptom, abnormal laboratory value) occurring after Xevudy administration, regardless of whether or not Xevudy is related to an AE. Considering whether or not the possibility of a reasonable relationship to Xevudy is present, the relationship to Xevudy will be assessed as "related" or "not related" by the investigator. The AEs assessed as "related" to Xevudy will be handled as an "ADR" suspected of being caused by Xevudy.
- ii). Among reported AEs, evens corresponding to the following A or B will be handled as a concern in the safety specification, "Serious Hypersensitivity such as Anaphylaxis and Infusion Reaction ".
 - A) Events which exclude both High Level Term (HLT) "Injection Site Reactions " and HLT "Infusion Site Reactions " from "Hypersensitivity (narrow)" in SMQs
 - B) "Anaphylactic reaction" (broad) in SMQs

9. Analysis Items and Methods

The detailed content of analysis will be separately specified in the Statistical Analysis Plan.

- 1. Analysis items
 - 1) Patient disposition-related matters
 - i) Number of enrolled patients and number of patients whose CRF data are collected and locked
 - Number of patients included in the safety analysis set and number of patients included in the clinical outcomes analysis set, numbers of patients excluded from safety and clinical outcomes analysis set and the reasons for exclusion
 - 2) Safety-related matters
 - i) Occurrence of ADRs (type and seriousness of ADRs, and incidence rate of patients with ADRs, etc.)
 - ii) Occurrence of an event defined as a concern included in the safety specification
 - 3) Clinical outcomes-related matters
 - i) <Inpatient only>Proportion of non-responders

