Among the patients who can be assessed for the following items a) to e) from Day 1 to the end of observation period, the following patients will be defined as "not effective" if applicable to any of a) to e). The proportion of non-responders is the proportion of patients assessed as "not effective" in the clinical outcomes analysis set.

- a) Patients who receive oxygen at a rate of <5L/min as a combination therapy for exacerbation of SARS-CoV-2 infection
- b) Patients who receive any of the following combination therapies for exacerbation of SARS-CoV-2 infection
 - Non-invasive positive pressure ventilation (NPPV)
 - Invasive mechanical ventilation (IMV) management
 - Extracorporeal membrane oxygenation (ECMO)
- c) Patients who require admission to HCU or ICU for exacerbation of SARS-CoV-2 infection in medical institutions with HCU or ICU
- d) Patients who are transferred to another hospital for exacerbation of SARS-CoV-2 infection to receive the treatments of a) to c) mentioned above
- e) Patients who result in death for exacerbation of SARS-CoV-2 infection
- ii) <Inpatient only> Distribution and transition of vital signs (Day 1, Days 2-15, Day 22, Day 29, discharge/transfer date)
- iii) <Inpatient only> Distribution and transition of clinical symptoms (Day 1, Days 2-15, Day 22, Day 29, discharge/transfer date)
- 2. Analysis methods
 - 1) Safety
 - i). The incidence rate of ADR patients will be calculated throughout the whole period, at Day 1, Days 2-15, Day 22, Day 29.
 - ii). The incidence rate of ADR-experiencing patients per 100 patient-years will be calculated along with 95% exact Poisson confidence intervals using chi-square distribution.
 - 2) Clinical outcomes

- i) The proportion of non-responders will be calculated (from Day 1 to the end of the observation period). The proportion of non-responders by sampling period for nucleic acid detection tests/antigen tests showing positive will be calculated.
- ii) The proportion of patient outcome at the end of the observation period in patients other than non-responders was be calculated.
- Summary statistics for vital signs will be calculated based on values at the time of measurement (Day 1, Days 2-15, Day 22, Day 29, discharge/transfer date). Also, summary statistics for vital signs by sampling period for nucleic acid detection tests/antigen tests showing positive will be calculated.

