- iv) For clinical symptoms, the incidence rate of patients with or without them will be calculated over time. Also, the incidence rate by sampling period for nucleic acid detection tests/antigen tests showing positive will be calculated.
- 3) Covariate consideration

The Robust (modified) Poisson regression model will be used to calculate the risk ratio and 95% confidence interval for each factor likely to affect safety (incidence rate of ADR patients) and clinical outcomes (proportion of non-responders), and to explore risk factors. For exploration of risk factor as appropriate, the unadjusted risk ratio and its 95% confidence interval will be calculated in univariate analysis. In the multivariate analysis, Spearman's correlation coefficient will be used first to confirm whether or not multicollinearity exists between factors, the missing values for each factor will be considered to select variables to be included in the model, and then the adjusted risk ratio and its 95% confidence interval will be calculated.

10. Organizational Structure

Refer to AT1

11. Name, Address of the Outsourcees, and the Scope of Outsourced Operations

- Enrolment and data management Outsourcee: CMIC Co., Ltd. ([name]) Scope: patient enrolment, EDC system development, data cleaning, other related operations
- Statistical analysis
 Outsourcee: CMIC Co., Ltd. ([name])
 Scope: statistical analysis, other related operations

12. Scheduled Timing to Be a Milestone for Assessing the Status and Results in the Study or Reporting to the Pharmaceuticals and Medical Devices Agency (PMDA) and Rationale

- At the time of Periodic Safety Reports: consideration will be comprehensively given to the safety and clinical outcomes information.
- At the time of re-examination application: the final report will be prepared/submitted, based on the results of tabulation and analysis obtained from the locked data of all collected CRFs.

13. Additional Measures that Have a Potential to Be Taken Depending on the Study Results and the Decision Criteria for the Start

The RMP, including the following, will be reviewed at the timings to be a milestone.

- Regarding the safety specification, if the incidence rate of patients experiencing ADRs, peak occurrence period and risk factors become visible as an ADR caused by Xevudy, the necessity for revising the Package Insert and study materials will be considered as appropriate.

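### The ADR sub-periods reuse the vital-sign and symptom observation days, so ADRs starting on Days 16-21 or 23-28 fall in no sub-period and the by-period profile is incomplete

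*Protocol*

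**What the plan says.** For safety, Section 9 (2. Analysis methods, 1) Safety, item i) plans: "The incidence rate of ADR patients will be calculated throughout the whole period, at Day 1, Days 2-15, Day 22, Day 29". Item ii adds an ADR rate per 100 patient-years with exact Poisson limits.

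Follow-up is set in Section 6: "The observation period per patient will be between Day 1 to 29 counting the date of Xevudy administration as Day 1". Two groups leave earlier. For inpatients: "If inpatients have been discharged/transferred from hospital before Day 29, they will be observed until the discharge/transfer date". For the rest: "For outpatients, the observation will be conducted on Day 1 only".

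Adverse events are not tied to visit days. In Section 8, item 14, "the investigator will collect the information about all AEs (e.g., a disease, symptom, abnormal laboratory value) occurring after Xevudy administration", and the recorded fields include the onset date: "Presence or absence of AEs after Xevudy administration, diagnosis or symptoms, occurrence date, outcome of AEs". The study schedule in Section 8 shows AE collection as a continuous arrow.

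Vital signs in inpatients follow a fixed list in Section 8: "date of measurement at Day 1, Days 2-15 (every day), Day 22, Day 29 and the" day of discharge or transfer. Clinical symptoms use the same list.

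Section 13 mentions the timing of reactions as one consideration for the safety specification: "if the incidence rate of patients experiencing ADRs, peak occurrence period and risk factors become visible as an ADR caused by Xevudy".

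**The concern.** The day list suits measurements taken only on set days. A temperature is recorded on Day 22 and there is no scheduled value for Day 18, so a single-day label loses nothing. ADRs are different, because an event can start on any day and its date is recorded. Applied to onset dates, the same list leaves gaps. An ADR starting on Day 18 is in the whole-period count and in none of the sub-periods.

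Two things follow. The sub-period counts need not account for every patient with an ADR, so the table cannot be reconciled with its own total. The profile after Day 15 also rests on two isolated days, so later onset can look rarer than it was. What is at stake is the description of when ADRs occur. The headline ADR incidence is not affected.

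**Working it through.** **Inputs from the protocol**

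- Observation period: Day 1 plus the 28 days from Day 2 (Section 6).
- ADR sub-periods: Day 1; Days 2-15; Day 22; Day 29 (Section 9).
- Vital-sign and symptom days: the same four entries plus the discharge or transfer date (Sections 8 and 9).
- AE onset date and end date of observation: both recorded (Section 8, items 14 and 11).

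**Step 1. Reproduce the stated length.** 1 + 28 = 29 days, which agrees with Days 1-29.

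**Step 2. Days covered.** 1 + 14 + 1 + 1 = 17 days. Reading Days 2-15 as fourteen daily entries instead of one window gives the same coverage.

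**Step 3. Days not covered.** 29 - 17 = 12 days: Days 16-21 (6) and Days 23-28 (6).

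- Share of the observation period: 12/29 = 41%.
- Share of the days after Day 15: 12/14 = 86%.

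**Step 4. Could Day 22 and Day 29 mean something wider?** The protocol never defines them as Days 16-22 and Days 23-29. A cumulative reading (up to Day 22, up to Day 29) does not fit either, because Days 2-15 starts afresh after Day 1. The sentence writes a range where it means a range, and then names two single days.

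**Step 5. Who can be affected.** Outpatients contribute Day 1 only. Inpatients who leave by Day 15 contribute no uncovered day. Only inpatients still observed on Day 16 or later can have an ADR in the gap.

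**Step 6. Range for the share of post-Day-1 ADRs missed.** The documents do not give lengths of stay, so the following are assumptions. With a constant ADR rate per day under observation,

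share missed = uncovered days observed / all days observed after Day 1.

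| Assumed follow-up of inpatients | Calculation | Share missed |
|---|---|---|
| None observed past Day 15 | 0 | 0% |
| 5% to Day 29, others 7 days after Day 1 | 12×0.05 / (28×0.05 + 7×0.95) = 0.60/8.05 | 7% |
| 10% to Day 29, others 7 days after Day 1 | 12×0.10 / (28×0.10 + 7×0.90) = 1.20/9.10 | 13% |
| All to Day 29 | 12/28 | 43% |

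A rate that falls with time since infusion would lower these figures, and a rising one would raise them.

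**Step 7. Check the remedy.** Day 1, Days 2-15, Days 16-22 and Days 23-29 give 1 + 14 + 7 + 7 = 29 days, each covered once.

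**The case against.** The strongest reply is that Section 9 leaves analysis detail to the SAP, which is not shown and may define proper windows. That would be a full answer if the protocol were silent. It is not silent: it lists the periods, and a SAP with contiguous windows would depart from that list. The protocol sentence needs correcting in either case.

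Four further objections stand. Each limits what a reader might infer.

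- **That the by-period rates are wrong.** Each rate is correct for the days it names. The set is incomplete. The whole-period rate counts ADRs on every day, and neither it nor the patient-year rate uses the sub-periods.
- **That 43% of ADRs after Day 1 would be lost.** This needs every inpatient to be followed to Day 29 at a constant ADR rate. Section 6 ends observation at discharge or transfer, so the true share may be far smaller, or nil.
- **That all incidence after Day 1 is understated because outpatients stay in the denominator.** The protocol names no denominator for the sub-periods and gives no outpatient share. A halving, such as 6/600 = 1.0% against 6/300 = 2.0%, would need both the full safety set as denominator and a half-and-half split. Neither is stated.
- **That this table drives a package-insert decision.** Section 13 speaks of the safety specification, leaves revision to consideration, and does not name this table as its source. Onset dates are recorded, so a peak period could be read from them directly. The table is simply the only analysis of ADR timing that the protocol sets out.

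**Conclusion.** The point holds as a gap in a stated rule. The listed sub-periods leave 12 of 29 days, and 12 of the 14 days after Day 15, without a place in the by-period table. This follows from the protocol's text and needs no assumption beyond reading Day 22 and Day 29 as single days, as they are written.

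The consequence is an incomplete time profile for inpatients still observed after Day 15. How many ADRs that concerns cannot be worked out from the protocol: the illustrations run from 0% to 43% of ADRs after Day 1, and the low end is entirely possible. The primary endpoint is intact and no data are lost. The correction is worth making because it is nearly free and lets the table reconcile with its total. The documents do not support treating it as a threat to the study's main safety result.

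**What to change.** In Section 9, analysis methods, safety item i, replace the day list with contiguous windows by date of onset: Day 1, Days 2-15, Days 16-22, Days 23-29, and the whole period.

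In the same sentence, name the denominator for each window as the patients still under observation when the window opens. Outpatients then count for Day 1 only, and inpatients count until discharge or transfer. This completes the definition of the windows and does not repair a separate error.

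The cost is one sentence in the protocol and the matching SAP table. Onset date and end date of observation are already on the case report form, so nothing new is collected. The sponsor would need to judge whether the edit counts as minor under Section 15, item 1, which otherwise calls for prior submission to the PMDA. The vital-sign and symptom time points can stay as they are.

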XEVUDY General Drug Use Investigation (SARS-CoV-2 Infection)

Protocol

GlaxoSmithKline K.K.

Prepared: 26 Oct. 2022 (Ver. 3.0)

1.	Objectives1
2.	Safety Specification1
3.	Target Population1
4.	Target Sample Size and Rationale1
5.	Planned Number of Medical Institutions by Department1
6.	Study Period1
7.	Study Methods2
8.	Study Items
9.	Analysis Items and Methods6
10.	Organizational Structure7
11.	Name, Address of the Outsourcees, and the Scope of Outsourced Operations
12.	Scheduled Timing to Be a Milestone for Assessing the Status and Results in the Study or Reporting to the Pharmaceuticals and Medical Devices Agency (PMDA) and Rationale
13.	Additional Measures that Have a Potential to Be Taken Depending on the Study Results and the Decision Criteria for the Start
14.	Publication of the Study Results
15.	Other Requirements
16.	Attachments
Adv	verse Events (AEs)10

1. Objectives

The objective of this study is to collect and assess the following information about safety and clinical outcomes of Xevudy in patients with severe acute respiratory syndrome coronavirus 2 (SARS-CoV-2) infection who have risk factors for progression to severe SARS-CoV-2 infection and do not require oxygen administration (OA) in daily clinical practice.

Primary endpoint;

• Occurrence status of adverse drug reactions (ADRs)

Secondary endpoint;

• Proportion of non-responders, and distribution and transition of vital signs and clinical symptoms

2. Safety Specification

In this study, the concern included in the safety specification is as follows;

• Serious Hypersensitivity such as Anaphylaxis, Infusion Reaction

3. Target Population

Among patients with SARS-CoV-2 infection which is Xevudy's indication, patients who have risk factors for progression to severe SARS-CoV-2 infection and do not require OA for SARS-CoV-2 infection at the beginning of Xevudy administration and receive Xevudy for the first time will be included in the study.

4. Target Sample Size and Rationale

- 1) Target number of patients: 630 (as enrolled patients)
- 2) Rationale:

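### The only confidence interval stated for ADR incidence is on a patient-year rate that pools one-day outpatients with inpatients observed for up to 29 days, so it depends heavily on inpatient share and length of stay

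*Protocol*

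**What the plan says.** Protocol section 1 names the primary endpoint as "Occurrence status of adverse drug reactions (ADRs").

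Section 9, 2.1) gives two summaries of it. Item i) is a proportion by period, with no interval stated: "The incidence rate of ADR patients will be calculated throughout the whole period, at Day 1, Days 2-15, Day 22, Day 29". Item ii) is a person-time rate with an interval: "The incidence rate of ADR-experiencing patients per 100 patient-years will be calculated along with 95% exact Poisson confidence intervals using chi-square distribution". Neither item is split by inpatient or outpatient status. The other intervals involving ADRs, in section 9, 2.3), are on risk ratios for candidate factors ("calculate the risk ratio and 95% confidence interval for each factor likely to affect safety (incidence rate of ADR patients")), not on the incidence itself.

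Section 6 sets the observation windows:
- General rule: "The observation period per patient will be between Day 1 to 29 counting the date of Xevudy administration as Day 1".
- Inpatients who leave early: "If inpatients have been discharged/transferred from hospital before Day 29, they will be observed until the discharge/transfer date".
- Outpatients: "For outpatients, the observation will be conducted on Day 1 only".

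The protocol neither fixes nor predicts the share of inpatients. Section 8, item 5 records the dose as one infusion, and section 2 names serious hypersensitivity, including infusion reaction, as the safety concern. The planning figure in section 4 is a proportion of patients: "within Xevudy group for 29 days was 1.7% (9/523 patients").

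**The concern.** Events divided by pooled patient-years summarise risk well when the hazard is roughly constant over the time counted. Here the counted time has two very different parts. Day 1 is contributed by everyone and contains the infusion. Days 2 to 29 are contributed by inpatients only, and only until they leave hospital. If ADRs cluster near the infusion, each further inpatient day enlarges the denominator and adds few events. The rate and both of its limits then fall as the inpatient share or the length of stay rises, with no change in the drug's risk.

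Section 15 requires results in repeated periodic safety reports, and section 13 ties review of the risk management plan to ADR findings. If the mix of settings shifts between reports, the patient-year rate could show an apparent change in safety or mask a real one.

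**Working it through.** **Plan's own figures.** The protocol gives no patient-year figure to reproduce. Its planning rate is 9/523 = 1.72%. The 600 patients in section 4 can be recovered on the proportion scale. A one-sample normal-approximation test (two-sided 5% assumed, 80% power, odds ratio 2) needs 606 patients from 1.7% and 599 from 9/523. The plan was therefore sized on proportions, not on person-time.

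**Inputs.** N = 600 (section 4). Outpatient observation is 1 day and inpatient observation is L days, with L at most 29 (section 6). Assumptions: x = 10 ADR patients, inpatient share q, and L = 29 or 10. Longer observation adds no ADRs, and person-time is not stopped at the first ADR.

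**Formulas.**
- Patient-days = N × [(1 − q) × 1 + q × L]; patient-years (PY) = patient-days / 365.25.
- Rate per 100 PY = 100 × x / PY.
- Exact Poisson limits per 100 PY: 100 × χ²(0.025; 2x) / (2 PY) and 100 × χ²(0.975; 2x + 2) / (2 PY).

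**Results for 10 ADR patients in 600.**

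| Inpatient share | Stay (days) | Patient-days | PY | Rate per 100 PY (95% CI) |
|---|---|---|---|---|
| 0% | – | 600 | 1.64 | 608.8 (291.9–1119.5) |
| 25% | 29 | 4,800 | 13.14 | 76.1 (36.5–139.9) |
| 50% | 29 | 9,000 | 24.64 | 40.6 (19.5–74.6) |
| 75% | 29 | 13,200 | 36.14 | 27.7 (13.3–50.9) |
| 100% | 29 | 17,400 | 47.64 | 21.0 (10.1–38.6) |
| 25% | 10 | 1,950 | 5.34 | 187.3 (89.8–344.5) |
| 75% | 10 | 4,650 | 12.73 | 78.5 (37.7–144.5) |
| 100% | 10 | 6,000 | 16.43 | 60.9 (29.2–112.0) |

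- From 25% to 75% inpatients, 29-day stays: 13,200 / 4,800 = 2.75-fold.
- From 25% to 75% inpatients, 10-day stays: 4,650 / 1,950 = 2.4-fold.
- Extreme bound, 0% against 100% inpatients all staying to Day 29: 17,400 / 600 = 29-fold. It becomes 28.5-fold if person-time stops at a Day 1 ADR.

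The proportion is 10/600 = 1.67% (Clopper-Pearson 95% CI 0.80–3.04%) in every row. That constancy follows from holding x fixed.

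**Relaxing the fixed count.** Let the daily ADR risk be a on Day 1 and b on each later day. To a close approximation, the pooled rate per patient-day is [a + q(L − 1)b] / [1 + q(L − 1)]. This is a weighted average of a and b, with weights set by q and L. With L = 29, the ratio of the rate at 25% to that at 75% inpatients is [(a + 7b)/8] / [(a + 21b)/22]. It is 22/8 = 2.75 when b = 0 and 1 when b = a. The pooled rate is free of the mix only under a constant hazard.

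**Ranking can reverse.** Suppose outpatients have a 1% ADR risk on Day 1 and inpatients a 2% risk over 29 days. The rates are 1 × 365.25 = 365 and 2 × 365.25 / 29 = 25 per 100 PY. The group with twice the recorded risk shows a rate 29/2 = 14.5 times lower.

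**The case against.** **The proportion is already planned.** Item i) comes first and includes Day 1 and the whole period. Nothing ranks the patient-year rate above it, and section 13 does not mention patient-years. This stands. A reader might infer that the patient-year rate is the study's main safety result, but the protocol does not say so.

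**Details belong to the SAP.** Section 9 defers them there, and the SAP is not at hand. It may add a binomial interval or a split by setting, so their absence from the protocol is not itself a fault. What remains is a choice the protocol does make: it attaches its one stated interval to a person-time measure across windows of 1 day and up to 29 days.

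**29-fold is unrealistic.** This stands. It compares 0% with 100% inpatients, all kept to Day 29, with no ADRs added. A protocol with inpatient-only outcomes and a separate outpatient rule expects a mix, so 2.4- to 2.75-fold is the fairer illustration.

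**Fixing the count builds in the answer.** This stands in part. If ADRs do arise after Day 1, the dependence weakens, and the whole-period proportion also moves with the inpatient share, because outpatients are not observed then. That favours Day 1 as the common window and does not rescue the pooled rate.

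**Comparison with 1.7%.** A reader might infer that the all-ADR proportion, once given an interval, could be set against 1.7%. The documents do not support this. That figure counts Hypersensitivity (narrow) SMQ events over 29 days, whereas the primary endpoint counts any event judged related. The safety-specification events in section 8, item 14 are drawn from reported AEs under a further definition.

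**Conclusion.** The point holds as a fault in the choice of measure, moderate in size. Following section 9, 2.1) ii) as written gives an interval on ADR incidence that depends heavily on inpatient share and length of stay. Over inpatient shares of 25% to 75%, the rate for the same 10 ADR patients in 600 differs by a factor of 2.4 (10-day stays) to 2.75 (29-day stays); 29-fold is only the outer bound. These sizes assume that ADRs occur near the infusion and that longer observation adds none. They shrink towards no effect as the hazard approaches constancy, which is unlikely after a single infusion with this safety concern. The inpatient shares and the 10-day stay are also assumptions, since the protocol gives neither.

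The point does not show that the safety assessment is lost: the ADR proportion is planned overall and at Day 1, only without a stated interval.

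**What to change.** In section 9, 2.1), or in the SAP if the protocol wording is brought into line:

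1. Attach exact (Clopper-Pearson) 95% intervals to the item i) proportion at Day 1 in all patients, the one window common to everyone.
2. Do the same for the proportion from Day 1 to end of observation in inpatients. State that this window is cut at discharge or transfer, which may depend on recovery, so it should not be read as a complete 29-day risk.
3. Show the patient-year rate only by inpatient and outpatient stratum, labelled supplementary.
4. Do not compare the all-ADR proportion with 1.7%. Any such comparison should use the safety-specification events in inpatients and state the differences in event definition and observation window.

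Section 8 already collects hospitalization status, event dates and end of observation. The cost is wording and one extra table, with no new data.
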